4. C-SSRS
5. Routine serum chemistries with liver function tests
6. Routine hematology tests with coagulation tests

Statistical Considerations**Data Analysis**

This is a within-subject, controlled open-label study seeking to determine the safety and tolerability of EPI-589 in patients with PD as well as to determine if EPI-589 can alter the biochemical signature of PD as assessed by peripheral blood biomarkers, CNS biomarkers, brain imaging biomarkers, and urine biomarker analysis. In addition, data on a number of disease-relevant clinical measures will be collected.

Space Intentionally Left Blank

II. SCHEDULE OF ASSESSMENTS AND DOSING SCHEDULE

Tests	-2 to -1 Months		Day0		Month 1	Month 2	Month3 End of Treatment Visit	Post-Treatment Follow-up
	Screening	Run-in (upto 30 days from screening2)						
Informed consent				Day 1 First Dose				
Inclusion/Exclusion criteria								
Past Medical history								
Previous genetic testing review								
Physical exam & Vital signs	b							
Height & weight	g		-					
12-lead ECG			-					
Hematology (including coagulation panel)			a,f					
Serum Chemistry			a,f					
Pregnancy test"								
C-SSRS								
Montreal Cognitive Assessment								
DaTscan (for idiopathic subjects)								
Revised Hamilton Rating Scale for Depression								
Subject enrolls in study		X						
Fasting blood-based glutathione cycle biomarkers								
Fasting Lumbar puncture (CNS biomarkers)								
Fasting Urine-based biomarkers								
MDS-UPDRS								
Timed motor tests (for subjects on dopa-amine therapy)								
NMSS, PDQ-39, EQ-5D								
BDI, MADRS								
Dmg plasma concentration ^o					c	c		
AE/SAE assessment	•	•	•		d	d	-	
Concomitant medications assessment					d	d	-	
Post-Treatment Assessments*								•

a. Screening values can be used if done within one month of baseline and if completed under fasted conditions

b. Female subjects of childbearing potential must have a negative pregnancy test.

c. Full plasma concentration profile will be obtained at Time= 0, and 0.5, 1, 2, 4, 6, 8, and 12 hours after dosing from the first 10 subjects to complete 1 month of therapy at each site. 12 hour PK can be obtained at time 0.

d. Month 2 assessments can be done by telephone. Any new AEs and associated concomitant medications reported at Month 3 must be followed for 30 days; this follow up may be conducted by telephone.

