This study will be conducted in full accordance with all applicable research policies and procedures, the EU Clinical Trials Directive, all applicable EU and US federal and local laws and regulations including 45 CFR 46, 21 CFR Parts 50, 54, 56, 312 and 314, and the Good Clinical Practice: Consolidated Guideline approved by the International Conference on Harmonization (ICH). Any episode of noncompliance will be documented.

The investigators will perform the study in accordance with this protocol, will obtain consent and will report AEs in accordance with local institutional policies and procedures and all EU and US federal requirements. Collection, recording, and reporting of data will be accurate and will ensure the privacy, health, and welfare of research subjects during and after the study.

I. Relevant Literature and Data

Literature references have been provided in Section **XV**. Additional information can be found in the Investigator's Brochure.

Space Intentionally Left Blank

IV. STUDY OBJECTIVES

A. Primary Objective

The primary objective of this study is to evaluate the effects of EPI-589 safety as assessed by occurrence of drug-related serious adverse events in subjects with PD.

B. Secondary Objectives

The secondary objectives are to evaluate the effects of EPI-589 in subjects with PD on:

1. Fasting glutathione cycle biomarkers as measured in blood, cerebral spinal fluid, and urine
2. Clinical disease state as assessed by the Movement Disorder Society-sponsored revision of the Unified Parkinson's Disease Rating Scale (MDS-UPDRS)
3. Disease morbidity as assessed by the Non-motor Symptoms Scale (NMSS), PDQ-39 and EQ-5D
4. Cognitive function as assessed by Montreal Cognitive Assessment (MoCA)
5. Mood as assessed by the Beck Depression Inventory (BDI) and the Montgomery & Asberg Depression rating scale (MADRS)
6. Pharmacokinetics
7. Hematology, blood chemistry, electrocardiogram

Space intentionally left blank

V. INVESTIGATIONAL PLAN

A. General Schema of Study Design

Following study enrollment, baseline assessments will be performed. Subjects will participate in a 30-day run-in phase to establish biomarker and clinical baseline measurements. EPI-589 will then be administered for up to 3 months (85 days \pm 3 days) unless discontinued for safety or tolerability issues.

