8. Age 40 to 75 years
9. Within 5 years of diagnosis of Parkinson's disease

For Genetic Subtype Subjects

10. A confirmed diagnosis of PD plus a genetic diagnosis consistent with PD, specifically PINK1, parkin, LRKK2 or other mitochondrial genetic subtype
11. Age 21 to 75 years

D2. Exclusion Criteria

1. Allergy to EPI-589 or other components of the EPI-589 tablet formulation
2. Use of antioxidant supplements, specifically vitamins E and C beyond the recommended daily allowance
3. Other Parkinsonian disorders
4. MoCA score of <24
5. Revised Hamilton Rating Scale for Depression ≥ 11
6. Parkinsonism due to drugs or toxins
7. Diagnosis of any other clinically significant neurologic disease that will confound the assessment of effect of study drug on disease progression
8. Malignancy within past two years
9. Pregnant or plans to become pregnant or breast feeding

10. History of stroke
11. History of brain surgery
12. Hepatic insufficiency with liver function tests (LFTs) > 3 times upper limit of normal
13. Renal insufficiency as defined by creatinine > 1.5 times normal
14. End stage cardiac failure
15. Participation within past 3 months and for duration of study in a trial of a device, drug or other therapy for PD

Space intentionally left blank

VI. STUDY PROCEDURES

A. Screening Visit

Screening evaluations will be performed within two months of first dose. The Investigator will inform each prospective subject of the nature of the study, explain the potential risks, and must obtain written informed consent from the subject prior to performing any study-related procedures and prior to the administration of study drug. Screening evaluations consist of the following:

1. Assessment of eligibility
2. Medical history, chart review
3. Receipt and review of previous testing including genetic tests
4. Physical examination* including vital signs
5. Height** and weight
6. 12-lead ECG
7. Laboratory assessments for hematology, coagulation, and serum chemistry*** (See Sections [VII.D2.a](#) and [VII.D2.b](#))
8. Urine pregnancy test (women of childbearing potential must have a negative urine pregnancy test; see Section [VII.D2.c](#))

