9. MDS-UPDRS
10. MoCA
11. DaTscan (for idiopathic subjects only)
12. Revised Hamilton Rating Scale for Depression
13. SAE assessments
14. Concomitant medications assessment (last 60 days prior to enrollment)

*Breast exam is at screening physical exam only.

** Height is measured at screening visit only.

***Screening values can be used if done within one month of baseline and if completed under fasted conditions

A1. Run-in Assessments

If the subject is eligible for the study following all screening procedures and is still willing to participate in the study, the subject must return to the clinic within one month for Run-in assessments. These will be performed 30 days (\pm 3 days) prior to baseline after eligibility is confirmed and subject is enrolled in the study. Run-in evaluations consist of the following:

1. Fasting blood-based glutathione cycle biomarkers
2. Fasting CNS biomarkers (lumbar puncture)
3. Fasting urine biomarkers
4. Timed motor tests (for subjects on dopamine therapy)
5. AE/SAE assessments
6. Concomitant medications review

B. Treatment Phase

After the Run-in phase, the subject must return to the clinic within 30 days (± 3 days) for baseline assessments. In-clinic study visits are scheduled at Month 1 and Month 3. The Month 2 study assessments can be conducted via telephone. End of treatment assessments will be conducted at the Month 3 study visit. Pharmacokinetic sampling takes place at Month 1 and Month 3. The baseline and all subsequent laboratory assessments should be obtained under fasting conditions.

B1. Baseline Assessments

The following will be assessed or performed at this visit.

1. Physical examination including vital signs
2. Height and weight*
3. 12-Lead ECG*
4. Fasting blood-based GSH cycle biomarkers
5. Fasting urine-based biomarkers
6. Laboratory assessments for hematology, coagulation and serum chemistry*
7. Urine pregnancy test (females of child bearing potential)
8. C-SSRS (Columbia Suicide Severity Rating Scale)

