9. MDS-UPDRS
10. NMSS, PDQ-39, EQ-5D
11. BDI, MADRS
12. Timed motor tests (for subjects on dopamine therapy)
13. AE/SAE assessments
14. Concomitant medications review

* Screening results for these assessments may be used if obtained within 1 month of Baseline and if they are completed under fasted conditions. The baseline laboratory assessments should be obtained under fasting conditions.

B2. Study Visit Assessments

- Month 1 Clinic Visit (Day 29 \pm 3 days):

The following will be assessed or performed at the Month 1 clinic visit:

1. Physical examination including vital signs
2. Height and weight
3. 12-lead ECG
4. Laboratory assessments for hematology, coagulation, and serum chemistry*
5. Urine pregnancy test (females of child bearing potential)

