In this subject-controlled, open label study the incidence of drug related SAEs in addition to changes from baseline to Month 3 for disease-relevant peripheral and CNS biomarkers as well as clinical measures will be calculated for each subject.

A1. Analysis Populations

Demographic characteristics and baseline efficacy data will be presented and summarized by treatment group for all subjects in the efficacy intent to treat (EITT) population. Demographic information will also be summarized by treatment group for the Safety population. No formal statistical comparisons will be made for either the EITT or Safety populations.

B. Efficacy Analysis

B1. Efficacy Variables

The efficacy variables in this study are:

1. Fasting blood-based glutathione cycle biomarkers
2. Fasting CNS biomarkers
3. Fasting urine-based biomarkers

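### MoCA, the only cognitive measure, has no Day 0 value: its change to Month 3 must start from the screening score that also decides entry

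*Protocol*

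**What the plan says.** All references are to the current protocol (Amendment 5.0).

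- **Objective and variable.** Secondary objective 4 (Section IV.B) is cognitive function, and MoCA is the only instrument named for it. MoCA is item 8 of the efficacy variables in VIII.B1.
- **Analysis rule.** VIII.A states that "changes from baseline to Month 3 for disease-relevant peripheral and CNS biomarkers as well as clinical measures will be calculated for each subject".
- **When MoCA is done.** It is item 10 of the screening list (VI.A) and item 13 of the Month 3 list (VI.B2). It is not in the run-in list (VI.A1), the 14-item Baseline list (VI.B1) or the Month 1 list (VI.B2).
- **What the Baseline list does contain.** MDS-UPDRS, then "10. NMSS, PDQ-39, EQ-5D", then BDI and MADRS, and the timed motor tests.
- **Eligibility.** Exclusion criterion 4 (V.D2) is "MoCA score of <24".
- **Carry-over of screening values.** The VI.B1 footnote says "Screening results for these assessments may be used if obtained within 1 month of Baseline and if they are completed under fasted conditions". It is attached only to height and weight, ECG and laboratory tests.
- **Timing.** After screening, "the subject must return to the clinic within one month for Run-in assessments" (VI.A1; the schedule gives up to 30 days). After run-in, "the subject must return to the clinic within 30 days (± 3 days) for baseline assessments" (VI.B). VI.A separately limits screening to two months before first dose.

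**The concern.** The trial has one arm, so each subject's pre-dose value is the only comparator. For MoCA that value has two weaknesses that the other clinical scales do not share.

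First, the score that starts the change is the score that admitted the subject. A candidate whose true level is near the cut-off gets in on a chance-high score and is turned away on a chance-low one. Among those admitted, a retest is therefore expected to be somewhat lower even if nothing has happened.

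Second, the interval takes in the whole screening and run-in period off drug. The other scales are measured from Day 0.

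MDS-UPDRS shows that repetition was feasible. It includes the Hoehn and Yahr stage used for entry, is done at screening, and is done again at baseline. MoCA also governs entry but is not repeated.

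At stake is how well a secondary objective can be read. The primary endpoint (drug-related SAEs) and the adaptive enrolment, which depends on biomarker response, are not affected.

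**Working it through.** The protocol states no figure for MoCA (no sample size, SD or expected change), so there is nothing to reproduce. The check has three parts.

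**1. Visit lists side by side (Section VI)**

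| Measure | Screening | Run-in | Day 0 | Month 1 | Month 3 |
|---|---|---|---|---|---|
| MoCA | yes | no | no | no | yes |
| MDS-UPDRS | yes | no | yes | yes | yes |
| NMSS, PDQ-39, EQ-5D | no | no | yes | no | yes |
| BDI, MADRS | no | no | yes | no | yes |

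The tick marks of the current schedule table were not legible in the text available, so this rests on the Section VI lists. The superseded Amendment 2.0 schedule also shows MoCA at screening and Month 3 only.

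**2. Length of the untreated stretch**

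- Longest by visit windows: 30 days (screening to run-in) + 33 days (run-in to baseline, 30 + 3) = 63 days.
- Limit in VI.A: two calendar months before first dose is 59 to 62 days, depending on the months. First dose may be on the day of the baseline visit. A gap of 63 days therefore always breaks this limit, by 1 to 4 days, and the longest gap that satisfies both rules is about 62 days.
- Shortest: 27 days (30 - 3), if run-in follows screening at once.
- Month 3 falls on Day 82 to 88 (85 ± 3).
- Untreated share of the MoCA interval, lowest: 27 / (27 + 88) = 27/115 = 23.5%.
- Untreated share, highest: 62 / (62 + 82) = 62/144 = 43.1%.

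**3. Regression from the cut-off (illustration only)**

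Scores of 24 or more are admitted, so with a continuity correction the cut is 23.5. For a normal screening score with mean m, standard deviation SD and retest correlation r, the expected retest change with no true change is

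-(1 - r) × SD × φ(a) / (1 - Φ(a)), where a = (23.5 - m)/SD.

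All of m, SD and r are assumptions.

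| m, SD | a | Share failing on MoCA | r = 0.6 | r = 0.8 | r = 0.9 |
|---|---|---|---|---|---|
| 25, 3 | -0.50 | 31% | -0.61 | -0.31 | -0.15 |
| 26, 2.5 | -1.00 | 16% | -0.29 | -0.14 | -0.07 |
| 27, 2 | -1.75 | 4% | -0.07 | -0.04 | -0.02 |

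Worked case, m = 26, SD = 2.5, r = 0.6: φ(-1)/(1 - Φ(-1)) = 0.242/0.841 = 0.288, and -0.4 × 2.5 × 0.288 = -0.29.

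For scale, if the SD of change is assumed to be 2, the standard error of a mean change in 40 subjects is 2/√40 = 0.32. Most of the table lies below one standard error. The largest entry is 0.61/0.32 = 1.9 standard errors.

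**The case against.** **Baseline need not mean the Day 0 visit.** The same sentence in VIII.A covers CNS biomarkers, and lumbar puncture is done at run-in and Month 3, not at Day 0. V.A also describes the run-in as a source of baseline measurements. A reader might infer that the protocol flatly contradicts itself on MoCA. The documents do not support that, because a last-pre-dose definition is a consistent reading and a statistical analysis plan may adopt it. This stands, and it softens the point. But such a definition only gives the screening score a label. It does not create a score nearer to dosing or undo the selection on that score.

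**The bias is probably small.** This also stands. The largest figure needs an unselected mean so close to the cut-off that about 31% of candidates would fail on MoCA alone. The net direction is not known either, since learning on retest would push the change upward.

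**Little hangs on it.** MoCA is one of twelve efficacy variables, VIII.A1 plans no formal comparisons, and no MoCA test or decision rule is stated. A reader might infer that the trial cannot say whether cognition changed. That goes too far. Attribution to the drug is already limited by the single-arm, open-label design, and a Day 0 MoCA would not remove that limit. What remains is that the MoCA change will be harder to read than the other scales.

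**The gap is not 63 days.** A reader who adds the windows would get 63, but the limit in VI.A rules that out. The supportable statement is up to about two months.

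**Conclusion.** The concern holds in a limited form. MoCA has no Day 0 value, and nothing in the protocol carries the screening score forward as baseline. The only available starting value is the score on which subjects were selected, taken between about four weeks and two months before Day 0. The change from it combines change during treatment, regression after selection, and an untreated period of roughly 24-43% of the interval.

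The visit lists and the interval share come from the protocol's own text. The size of the regression, about 0 to -0.6 points, rests wholly on assumed values for the mean, SD and retest correlation, and is an illustration and not an estimate. This is a worthwhile, inexpensive improvement to a secondary objective, not a flaw that defeats it.

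**What to change.** Add MoCA to the Baseline list in VI.B1 and to the Day 0 column of the schedule, with a version different from the screening one where available. State that the Day 0 score is the comparator for Month 3 and that the screening score serves eligibility only. The gap from the pre-dose score to Day 0 then falls to zero, and the comparator is no longer the selecting score.

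Reconcile the visit windows (VI.A1, VI.B and the schedule, 63 days in total) with the two-month limit in VI.A.

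The cost is one short questionnaire at a visit that already includes MDS-UPDRS, NMSS, PDQ-39, EQ-5D, BDI and MADRS. The downside is a few more minutes per subject and one more exposure to the test before dosing, so some retest learning remains possible.

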4. MDS-UPDRS
5. NMSS
6. PDQ-39
7. EQ-5D
8. MoCA
9. BDI
10. MADRS
11. Timed motor tests as ON state only (for subjects on dopamine therapy)
12. Pharmacokinetics

C. Safety Analysis

The primary objective of this study is to evaluate the effects of EPI-589 safety as assessed by occurrence of drug-related serious adverse events in subjects with PD.

Assessment of safety will include calculating the overall number of subjects (by absolute number and percentage) with a particular AE. Safety will also be evaluated through examining clinical laboratory data (including chemistry and hematology and coagulation information) and physical examination findings, including vital signs obtained throughout the course of the study. A medical monitor will provide study oversight.

D. Sample Size

Approximately 40 subjects (20 with genetically-defined subtypes of PD and 20 idiopathic PD subjects). Under an adaptive design strategy, additional subjects (up to 20) may be added to increase the number of biomarker-responsive idiopathic PD subjects to achieve a higher number of subjects in whom we could understand the biochemical effects of the investigative drug and its potential clinical impact as assessed by the same study protocol and outcome metrics.

Space intentionally left blank

IX. STUDY MEDICATION

A. Description

EPI-589 is presented as an immediate release film-coated tablet. Each tablet contains 250 mg of EPI-589 and the following compendial excipients: lactose, microcrystalline cellulose, polyvinylpyrrolidone, crospovidone and magnesium stearate. Each tablet is film-coated with Opadry® II yellow. The tablets are yellow-colored and oval-shaped with a total target weight of 824 mg. The tablets are packaged at 28 tablets per bottle in high-density polyethylene (HDPE) pharmaceutical wide mouth containers, induction sealed, and closed with a child-resistant closure. Each container is labeled with appropriate product information meeting current regulatory requirements.

B. Packaging

B1. Labeling

Each container is labeled with appropriate product information meeting current regulatory requirements, in compliance with 21 CFR 312.6 and Eudralex Vol. 4 EU Guidelines to Good Manufacturing Practice, Medicinal Products for Human and Veterinary Use, Annex 13

B2. Dosage Form

The EPI-589 drug product will be provided in a 250-mg tablet formulation.

B3. Dispensing

Tablets are packaged in white round HDPE wide mouth containers. Each container holds 28 tablets without desiccant. Each container is sealed with an induction seal held in place with a child-resistant closure. The packaged tablets are stored at controlled room temperature 20° to 25°C (68° to 77°F). (See United States Pharmacopeia [USP]).

C. Treatment Compliance and Adherence

Study medication will be counted to assess compliance during each scheduled clinic visit. Subjects who take \geq 80 percent of the prescribed doses and no more than 100 percent will be considered compliant. Subjects who fall outside the boundaries of these thresholds will be counseled and re-instructed on proper dosing procedures. Medication compliance will be recorded on the CRF for each visit after verification with subject-completed diary cards and returned used drug supply.

D. Drug Accountability

Dosing information will be captured on a subject Dosing Diary Form. This form is part of the source documentation and will be utilized as a source for the completion of CRFs associated with dosing and for reconciliation of study drug administered and returned to the study site for

accounting and destruction. Adequate records of study drug receipt and disposition should be maintained by pharmacy records of receipts, investigational drug orders, dispensing records, and disposition forms. The Study Monitor will also assess drug accountability and will review the pharmacy records and Investigator study file to assure the study medication is prescribed by the Investigator or designee for the purpose of this study. At study completion, all drug supplies including partially used and empty containers must either be returned to the Sponsor or designee or destroyed per study site guidelines for destruction of investigational product immediately after drug accountability is performed by the study monitor.

Space intentionally left blank

X. SAFETY MANAGEMENT

A. Clinical Adverse Events

Clinical AEs will be monitored throughout the study. All AEs, whether observed by the Investigator, reported by the subject, from clinically significant laboratory findings, or other means, will be recorded in the CRF.

B. Adverse Event Reporting

All SAEs will be reported to the IRB/ IEC in accordance with their policies and as detailed below.

BI. Safety Guidance

Based on the known clinical manifestations of Parkinson's disease, we expect that many AEs could occur during the course of the trial that are well documented to occur as the results of the natural history of this disease. These include, but are not limited to worsening neuromuscular function, depression, decline in cognitive function, loss of vision and other ophthalmological symptoms, loss of coordination and loss of speech.

As there are no data available regarding EPI-589 phototoxicity, investigators are to advise subjects to take measures to minimize exposure to ultraviolet (UV) light for the duration of the study and for one week after the last dose.

BioElectron Technology Corporation may request that the Investigator perform or arrange for the conduct of supplemental measurements and/or evaluations. If a subject dies during participation in the study or during a recognized follow-up period, BioElectron Technology Corporation should be provided with a copy of any post-mortem findings, including histopathology.

C. Definition of an Adverse Event

CI. Adverse Event

An AE is any untoward medical occurrence in a subject or clinical investigation subject administered a pharmaceutical product and which does not necessarily have to have a causal relationship with this treatment. An AE can therefore be any unfavorable and unintended sign (including an abnormal laboratory finding), symptom, or disease temporally associated with the use of a medicinal (investigational) product, whether or not related to the medicinal (investigational) product.

The AE may be:

1. A new illness
2. Worsening of a sign or symptom of the condition under treatment or of a concomitant illness

3. An effect of the study medication, including comparator
4. A combination of 2 or more of these factors

No causal relationship with the study medication or with the clinical study itself is implied by the use of the term “adverse event” or “AE”.

Surgical procedures themselves are not AEs; they are therapeutic measures for conditions that require surgery. The condition for which the surgery is required may be an AE. Planned surgical measures permitted by the clinical study protocol and the condition(s) leading to these measures are not AEs.

Adverse events fall into the categories “non-serious” and “serious”.

C2. Definition of a Serious Adverse Event (SAE)

An SAE is one that at any dose results in any of the following:

1. Death;
2. A life-threatening adverse drug experience;
3. Inpatient hospitalization or prolongation of existing hospitalization;
4. A persistent or significant disability/incapacity; or
5. A congenital anomaly/birth defect.

ICH guidance also recommends that important medical events that may or may not be immediately life-threatening or result in death or hospitalization should also be considered serious when, based upon appropriate medical judgment, they may jeopardize the subject or may require intervention to prevent one of the other outcomes listed in the serious definition.

The term “life-threatening” in the definition of “serious” refers to an event in which the subject was at immediate risk of death at the time of the SAE. It does not refer to an SAE which hypothetically might have caused death if it were more severe.

Medical and scientific judgment should be exercised in deciding whether other AEs, such as important medical events that may not be immediately life-threatening or result in death or hospitalization but may jeopardize the subject, require intervention to prevent one of the other outcomes listed above. These should also usually be considered serious. Examples of such events are intensive treatment in an emergency room or at home for allergic bronchospasm; blood dyscrasias, or convulsions that do not result in hospitalization; or development of drug dependency or drug abuse.

■ subjects who become pregnant should be immediately discontinued from the study if they have not yet received study drug. If a subject is found to be pregnant after ■ has received study drug, ■ should discontinue dosing, complete all end-of-study procedures, and be followed to determine the outcome of the pregnancy; follow-up of the pregnancy, fetus, and child will continue for at least 8 weeks after delivery. While pregnancy itself is not considered an AE or SAE, all pregnancies should be reported using the same process as for SAEs. Any

pregnancy complications or an outcome other than a healthy, normal outcome will be recorded as an AE or SAE.

Clarification on the difference in meaning between “severe” and “serious”: The term “severe” is often used to describe the intensity (severity) of a specific event (as in mild, moderate, or severe myocardial infarction); the event itself, however, may be of relatively minor medical significance (such as severe headache). This is not the same as “serious,” which is based on the outcome or action criteria usually associated with events that pose a threat to life or functioning. Seriousness (not severity) serves as a guide for defining regulatory reporting obligations.

C3. Non-serious Adverse Event

A non-serious AE is any AE not meeting the SAE criteria.

C4. Definition of Relationship to Study Medication

Association or relatedness to the study medication will be graded as either “probably”, “possibly”, or “unlikely”. Determination of relatedness includes:

PROBABLY – The adverse event:

1. Follows a reasonable temporal sequence from drug administration
2. Abates upon discontinuation of the drug and reappears with re-introduction of the drug
3. Cannot be reasonably explained by the known characteristics of the subject’s clinical state

POSSIBLY – The adverse event:

1. Follows a reasonable temporal sequence from drug administration
2. Could have been produced by the subject’s clinical state or by other modes of therapy administered to the subject

UNLIKELY – The adverse event:

1. Does not follow a reasonable temporal sequence from drug administration
2. Is readily explained by the subject’s clinical state or by other modes of therapy administered to the subject

C5. Definition of Severity

All AEs will be graded if possible by Common Terminology Criteria for Adverse Events (CTCAE) v4.03. The severity of AEs that cannot be graded by CTCAE v4.03 will be categorized as follows:

Grade 1 – Transient or mild discomfort; no limitation in activity; no medical intervention/therapy indicated.

Grade 2 – Moderate limitation in activity, some assistance may be needed; minimal noninvasive medical intervention/therapy indicated.

Grade 3 – Severe limitation in activity, assistance usually required; medical intervention/therapy required; hospitalization or prolongation of hospitalization indicated; disabling.

Grade 4 – Extreme limitation in activity, significant assistance required; urgent medical intervention/therapy required; life-threatening consequences.

Grade 5 – Death

C6. Definition of Unexpected Adverse Event

Any AE, the specificity or severity of which is not consistent with those listed in the current investigator's brochure is considered "unexpected."

C7. Notification of SAEs

The Investigator is responsible for promptly notifying the IRB/IEC of all study on-site SAEs and other unanticipated problems related to research.

External SAEs that are unexpected and related to the study intervention should be reported as they are received using the MedWatch or CIOMs form (as appropriate).

SAEs (whether unexpected or expected AEs) must be documented on the designated SAE form. The SAE must be reported to the medical expert and appropriate BioElectron Technology Corporation BioElectron-assigned pharmacovigilance staff within 24 hours, according to regulatory, Sponsor, or ICH-E6 Good Clinical Practice, followed by the SAE form within two calendar days. The designated SAE form and the instructions are provided in the Investigator's site file.

The SAE contact information will be provided separately from the protocol.

The Investigator and/or Medical Expert must also inform the Study Monitor and the Sponsor in all cases. Any SAEs must also be reported to the IRB/IEC. The Sponsor or designee will ensure that all legal reporting requirements are met.

The initial report must be as complete as possible, including details of the current illness and (serious) adverse event, and an assessment of the causal relationship between the event and the study medication.

Information not available at the time of the initial report (e.g., an end date for the AE or laboratory values received after the report) must be documented on a follow-up SAE forms.

The instructions to sites for the completion of SAE reports give detailed guidance on the reporting of SAEs and AEs initially reported as non-serious that become serious. When a non-serious event becomes serious, details must be forwarded immediately to the Medical expert and BioElectron Technology Corporation or BioElectron-assigned pharmacovigilance staff first for assessment and then submitted to the Sponsor on the designated SAE form within 24 hours.

All relevant information about suspected unexpected serious adverse reactions (SUSARs) that are fatal or life-threatening are to be recorded and reported to the relevant competent authorities.

In the US, all fatal or life-threatening suspected unexpected serious adverse events assessed as possibly or probably related to study drug by the Sponsor must be reported to the FDA as soon as possible (i.e., by telephone or facsimile transmission), but no later than 7 calendar days after first knowledge by the Sponsor that a report qualifies as a suspected unexpected fatal or life-threatening reaction. All unexpected serious adverse events, other than fatal or life-threatening, assessed as possibly or probably related to study drug by the Sponsor must be reported to the FDA within 15 calendar days from the day the Sponsor determines that the information qualifies as a SUSAR.

In the UK, the Sponsor or trial investigator must act immediately or at least within 24 hours after becoming aware of a SUSAR by informing the MHRA's Clinical Trial Unit by telephone. The MHRA must then be informed in writing within 3 days of the incident. All SUSARs originating in the UK or originating outside the UK involving the same medicinal product are to be reported. Fatal or life-threatening SUSARs are to be reported as soon as possible, but no later than after 7 days. Any additional relevant information must be sent within 8 days of the report. Non-fatal or non-life-threatening SUSARs are to be reported as soon as possible but no later than 15 days after becoming aware of the reaction.

C8. Follow-up Report

If an SAE has not resolved at the time of the initial report, a follow-up report including all relevant new or reassessed information (e.g., concomitant medication, medical history) should be submitted to the IRB/ IEC . All SAEs should be followed until either resolved or stable.

C9. Dose Modification Guidelines

In the event that any patient develops elevated INR \geq grade 2 in severity ($> 1.5-2.5 \times \text{ULN}$) per CTCAE criteria version 4.0 thought to be related to treatment with EPI-589, administration of EPI-589 will be reduced by 1/2 to 50 percent of the starting dose. Should the INR toxicity not resolve to at least grade 1 in severity within two weeks of the initial dose reduction, administration of EPI-589 may either be further reduced or discontinued.

Once a patient's dose is reduced due to elevated INR thought to be related to study drug administration, their dose should not be re-escalated.

D. Medical Emergencies

In medical emergencies, the Investigator should use medical judgment and remove the subject from the immediate hazard. The Medical Expert and the IRB/ IEC must be notified regarding the type of emergency and course of action taken and the procedures for SAE reporting must be followed.

D1. Emergency Sponsor Contact

In emergency situations, the Investigator should contact the Medical Monitor: [REDACTED]
[REDACTED]

D2. Emergency Treatment

At present, the threshold and extent of clinical adverse effects are not known as only limited information is available in healthy volunteers. It is anticipated in the planned study that any effects will be minimal and laboratory measurements will detect study drug effects before they become clinically significant.

Space intentionally left blank

XI. STUDY ADMINISTRATION

A. Treatment Assignment Methods

This is an open-label study.

B. Data Collection and Management

Monitoring and auditing procedures, developed or endorsed by BioElectron Technology Corporation will be followed in order to comply with GCP guidelines. Direct access to on-site study documentation including all source data, documentation and medical records should be ensured.

The study will be monitored by BioElectron Technology Corporation throughout the course of the study, the Study Monitor will make frequent contact with the Investigator. This will include telephone calls and on-site visits. During the on-site visits, the completed CRF will be compared to the source documentation for completeness, accuracy and adherence to the protocol. As part of the data audit, source documents must be made available to the Study Monitor for review. The Study Monitor will also perform drug accountability checks and will review the Investigator study file to assure completeness of documentation in all respects of clinical study conduct.

Upon completion of the study, the Study Monitor will arrange for a final review of the study files, after which the files should be secured for the appropriate time period. The Investigator, or appointed delegate, will meet with the Study Monitor during the on-site visits and will cooperate in providing the documents for inspection and responding to inquiries. In addition, the Investigator will permit inspection of the study files by authorized representatives of BioElectron Technology Corporation or the regulatory agencies.

US and other competent regulatory authorities, the IRB/IEC, and an auditor authorized by the Sponsor may request access to all source documents, CRFs, and other study documentation for on-site audit or inspection. Direct access to these documents must be guaranteed by the Investigator, who must provide support at all times for these activities. Medical records and other study documents may be copied during audit or inspection provided that subject names are obliterated on the copies to ensure confidentiality.

C. Data Quality Assurance

As a final step in the data management process, a 100% audit will be performed on the key safety and critical efficacy parameters. In addition, a random subject sample (10%) will be selected in order to perform a partial audit of remaining data. The purpose of this audit is to detect systematic and random errors. Any errors found from this audit will be corrected and, if the error rate is greater than 1 error per 1,000 fields (0.001%), a systematic review of the database will be undertaken and corrections will be made to achieve an error rate of less than 0.001%.

AEs will be coded using MedDRA, version (14.3). Prior and concomitant medications will be coded according to the World Health Organization (WHO) Drug Dictionary, March 2014.

D. Retention of Study Records

The following records must be retained by the Investigator for a *minimum* of 2 years after the Sponsor has notified the FDA or other competent authority that investigations have been discontinued, or after the FDA or other competent authority has approved the new drug application. In accordance with European regulatory requirements (Directive 2005/28/EC and Annex 17 and 2001/83/EC and Annex1), the Sponsor may request retention for a longer period of time.

1. Signed informed consent documents for all subjects
2. Subject identification code list, screening log (if applicable), and enrollment log
3. Record of all communications between the Investigator and the IRB/IEC
4. Composition of the IRB/IEC or other applicable statement
5. Record of all communications between the Investigator and Sponsor (or Contract Research Organization [CRO])
6. List of Sub-investigators and other appropriately qualified persons to whom the Investigator has delegated significant trial-related duties, together with their roles in the study and their signatures
7. Copies of CRFs and of documentation of corrections for all subjects
8. Drug accountability records
